**F. Modification of Pentoxifylline dosing:**

1. If toxicity is Grade 2, decrease dosage to 400 mg bid. If toxicity resolves or decrease to Grade 1, maintain at this lower dose. If toxicities are  $\geq$ Grade 3, stop Pentoxifylline and the patient should be removed from the study.
2. Discontinue if signs or suspicion of cardiovascular issues appear.

**G. Modification of drug dosing where side effect can't be attributed to one specific drug:**

1. Since the 3 study drugs have overlapping toxicities, circumstances may arise in which it is not clear which drug is responsible for the toxicity.
2. If the toxicities are  $\geq$ Grade 3, stop all 3 drugs and the patient should be removed from the study.
3. If toxicity is Grade 2, first reduce the dose of atorvastatin as per guidelines above. If after 1 week the toxicity has not decreased to Grade 1 or resolved, reduce the dose of Pentoxifylline as per guidelines above. If after an additional week the toxicity has not decreased to Grade 1 or resolved, reduce the dose of Vitamin E as per guidelines above. If after another week the toxicity has not resolved or decreased to Grade 1, all 3 drugs should be stopped and the patient should be removed from the study.

4. Cardiovascular issues: for toxicity of Grade 3 or higher, all 3 drugs will be discontinued, and the patient directed to the nearest emergency department for urgent evaluation. For toxicity of Grade 2, guidelines delineated in sections 8.G.1-3 above will be followed for drug dosing modifications, while concurrently obtaining a cardiovascular evaluation from the patient's cardiologist (if he has one), or his personal primary care physician. At the patient's preference, cardiology evaluation may be obtained at MD Anderson. Continuation on study medications will be contingent on cardiology approval.

## **9.0 Data Collection**

A. Collection of study data listed in the table in section 7 will be the responsibility of the research nurse at each study site.

B. Clinical study data for this trial will be collected and managed using the RedCap database within patient registry in the institution CORe database. RedCap is a secure portal that requires users to login with validated credentials. Electronic data will be stored on a password-protected computer. Paper data will be stored in a locked cabinet. Data will be maintained in the Radiation Oncology Clinical Research Office.

## **10.0 Adverse Events**

An adverse event is the appearance or worsening of any undesirable sign, symptom, or medical condition occurring after the first protocol intervention, even if the event is not considered to be related to study treatment. Medical conditions/diseases present before starting study therapy are only considered adverse events if they worsen after starting study treatment. Abnormal laboratory values or test results constitute adverse events only if they induce clinical signs or symptoms, are considered clinically significant, or require therapy.

The investigator (or physician designee) is responsible for verifying and providing source documentation for all adverse events  $\geq$  grade 2 and assigning the attribution for all adverse events  $\geq$  grade 2 for subjects enrolled.

---

#### Recommended Adverse Event Recording Guidelines

Attribution	Grade 1	Grade 2	Grade 3	Grade 4	Grade 5
Unrelated	Phase I				
			Phase II	Phase II	Phase II
				Phase III	Phase III
Unlikely	Phase I				
			Phase II	Phase II	Phase II
				Phase III	Phase III
Possible	Phase I				
	Phase II				
		Phase III	Phase III	Phase III	Phase III
Probable	Phase I				
	Phase II				
		Phase III	Phase III	Phase III	Phase III
Definitive	Phase I				
	Phase II				
		Phase III	Phase III	Phase III	Phase III

#### **Serious Adverse Event (SAE) Reporting**

An adverse event or suspected adverse reaction is considered “serious” if, in the view of either the investigator or the sponsor, it results in any of the following outcomes:

- Death
- A life-threatening adverse drug experience – any adverse experience that places the patient, in the view of the initial reporter, at immediate risk of death from the adverse experience as it occurred. It does not include an adverse experience that, had it occurred in a more severe form, might have caused death.
- Inpatient hospitalization or prolongation of existing hospitalization

- A persistent or significant incapacity or substantial disruption of the ability to conduct normal life functions.
- A congenital anomaly/birth defect.

Important medical events that may not result in death, be life-threatening, or require hospitalization may be considered a serious adverse drug experience when, based upon appropriate medical judgment, they may jeopardize the patient or subject and may require medical or surgical intervention to prevent one of the outcomes listed in this definition.

Examples of such medical events include allergic bronchospasm requiring intensive treatment in an emergency room or at home, blood dyscrasias or convulsions that do not result in inpatient hospitalization, or the development of drug dependency or drug abuse (21 CFR 312.32).

- Important medical events as defined above, may also be considered serious adverse events. Any important medical event can and should be reported as an SAE if deemed appropriate by the Principal Investigator or the IND Sponsor, IND Office.
- All events occurring during the conduct of a protocol and meeting the definition of a SAE must be reported to the IRB in accordance with the timeframes and procedures outlined in "The University of Texas M. D. Anderson Cancer Center Institutional Review Board Policy for Investigators on Reporting Serious Unanticipated Adverse Events for Drugs and Devices". Unless stated otherwise in the protocol, all SAEs, expected or unexpected, must be reported to the IND Office, regardless of attribution (within 5 working days of knowledge of the event).
- All life-threatening or fatal events, that are unexpected, and related to the study drug, must have a written report submitted within 24 hours (next working day) of knowledge of the event to the Safety Project Manager in the IND Office.

- Unless otherwise noted, the electronic SAE application (eSAE) will be utilized for safety reporting to the IND Office and MDACC IRB.
- Serious adverse events will be captured from the time of the first protocol-specific intervention, until 30 days after the last dose of drug, unless the participant withdraws consent. Serious adverse events must be followed until clinical recovery is complete and laboratory tests have returned to baseline, progression of the event has stabilized, or there has been acceptable resolution of the event.
- Additionally, any serious adverse events that occur after the 30 day time period that are related to the study treatment must be reported to the IND Office. This may include the development of a secondary malignancy.

**Reporting to FDA:**

- Serious adverse events will be forwarded to FDA by the IND Sponsor (Safety Project Manager IND Office) according to 21 CFR 312.32.

It is the responsibility of the PI and the research team to ensure serious adverse events are reported according to the Code of Federal Regulations, Good Clinical Practices, the protocol guidelines, the sponsor's guidelines, and Institutional Review Board policy.

**11.0 Biostatistics**

**A. Goal:**

The purpose of this trial and design is to provide inexpensive treatment for ED following XRT. While we hypothesize a smaller success rate than prescription ED treatments, this combination may be a less expensive alternative for those patients who do benefit. Three planned subgroups

will be enrolled, patients who are not on any statins at the time of enrollment, those on atorvastatin, and those on other statins. Patients will remain on study from enrollment until 1 year, disease relapse requires therapy, the physician withdraws the patient for safety reasons, or the patient withdraws for any reason.

Revision 2021. Since this trial was closed to accrual during the pandemic and new telemedicine practices and pandemic limitations are stifling accrual, this trial is being revised to enroll 50 patients with planned subgroups based on prior statin experience rather than the original 270 with 90 patients per statin cohort. This will still allow us to honor the patients already enrolled, learn something new, and also complete the trial in a reasonable amount of time under the new conditions. At the time of revision, there are 11 patients enrolled, and the first interim analyses as described in this revision allow the trial to continue.

## **B. Endpoints**

### **i. IIEF-5 (International Index of Erectile Function)**

This validated instrument will be completed as per study calendar. The instrument categorizes ED severity into 5 categories as none (22-25), mild (17-21), mild to moderate (12-16), moderate (8-11), or severe (5-7). A patient will demonstrate improvement at any time point if his score goes up enough to move at least 1 category less severe compared to baseline. A patient with improvement will be considered to have a response. Patients who drop out of the trial without any measurements will count as a non-responder.

### **ii. Adverse Events**

Patients' adverse events will be recorded by CTCAE v 4.03 at baseline and throughout this trial and at 30 days after stopping the active treatment portion of this trial (1 year on PAVE).

iii. Use of other ED treatment after PAVE.

ED treatment medications prescribed during or upon leaving this trial will be collected at 18 months

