### **3.0 Objectives**

A. **Primary Objective:** To estimate the proportion of patients who achieve a clinically significant improvement in erectile dysfunction (ED) when treated with a combination of Atorvastatin or patient's currently prescribed statin, Vitamin E, and Pentoxifylline (PAVE). Clinically significant improvement is defined as an improvement by one category, e.g., from mild-moderate to mild, on the IIEF-5 [International Index of Erectile Function] score, in men with established ED who have completed radiation therapy for prostate adenocarcinoma.

B. **Secondary Objectives**

- i. To report the safety profile of PAVE.
- ii. To report the rate of choosing other ED treatments after PAVE.

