**E. Analysis Plan**

Patients' baseline ED levels will be reported along with the proportion for patients who improve by at least 1 level according to the IIEF-5 for each time point measured. The proportion will be reported along with a 95% credible interval implementing a non-informative prior of beta(0.33, 0.67). Additionally, the proportion of patients who ever improve by at least 1 level will be reported overall. For secondary measures, the safety profile of the PAVE combination will be reported overall and for each planned subgroup based on prior statin treatment, with adverse events summarized by grade and time to onset to first grade 3 adverse event. Finally, the number of patients who drop out of the study to start an ED prescription medication will be reported. Exploratory analyses will be utilized to determine whether baseline patient features can predict response to PAVE or adverse events.

The Investigator is responsible for completing an efficacy/safety summary report, and submitting it to the IND Office Medical Affairs and Safety Group, for review and approval. This should be submitted every 10 evaluable patients, complete 8 weeks of study treatment until enrollment is complete

A copy of the summary should be placed in the Investigator's Regulatory Binder under "sponsor correspondence".

Important medical events as defined above, may also be considered serious adverse events. Any important medical event can and should be reported as an SAE if deemed appropriate by the Principal Investigator or the IND Sponsor, IND Office.

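### The plan does not say how IIEF-5 scores count once another ED treatment has started, so if any such man stays on study the response rate is biased upward

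*Combined protocol and SAP*

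**What the plan says.** Section 3.0 sets the primary objective as the proportion of men who improve by one IIEF-5 category under PAVE. Section 1.0 makes each man his own control.

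Section 11.B.i compares the score at any time point with baseline and adds: "A patient with improvement will be considered to have a response". Section 11.D repeats that improvement at any on-trial time point suffices and that a responder never reverts. The only handling rule in 11.B.i is that men who leave with no measurements are non-responders. Exclusion item 8 in section 4.0 bars 5-PDE inhibitors at entry and for the preceding 30 days. It says nothing about later use.

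Other ED treatment appears in these places:

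- Section 3.0, secondary objective: "To report the rate of choosing other ED treatments after PAVE".
- Section 11.B.iii, heading: "Use of other ED treatment after PAVE". Text beneath it: "ED treatment medications prescribed during or upon leaving this trial will be collected at 18 months".
- Section 11.E: "the number of patients who drop out of the study to start an ED prescription medication will be reported".
- Section 11.A, reasons for coming off study. Besides reaching one year and relapse needing therapy, these include: "the physician withdraws the patient for safety reasons, or the patient withdraws for any reason". Starting another ED treatment is not named.

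Section 11.E also reports "the proportion for patients who improve by at least 1 level according to the IIEF-5 for each time point measured", as well as the overall proportion who ever improve.

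**The concern.** The primary result is meant to describe what PAVE does. Section 11.A itself states: "While we hypothesize a smaller success rate than prescription ED treatments". The sponsor therefore expects other ED drugs to work more often than PAVE. A man who has not responded to PAVE, adds such a drug and then moves up a category would be counted as a PAVE responder for good under the rule as written. There is no concurrent control arm in which the same thing would show.

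Two results are exposed: the overall ever-improved proportion and the futility count, which uses the same definition. The by-visit proportions would show a late rise but could not say whether it came from PAVE or from another drug.

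The timing may also be hard to recover. The other drugs are collected at 18 months, six months after the last scheduled IIEF-5, and no start date is asked for. Table 1 has no history and physical at 3 or 9 months, which are two of the four post-baseline IIEF-5 contacts, and the questionnaire may be completed at home.

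**Working it through.** **1. Do the passages settle whether such men stay on study?**

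- Toward leaving: the secondary objective and the 11.B.iii heading both place other treatment after PAVE, and 11.E describes men who drop out in order to start it.
- Toward staying: the text under 11.B.iii sets drugs prescribed *during* the trial beside those prescribed on leaving it.
- Neutral: 11.A lets a man withdraw for any reason but does not say that starting another treatment ends participation.

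The question is open, with the weight of the wording toward leaving.

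**2. Direction.** Response means ever improved and cannot be undone. Adding later scores to a man's record can turn a non-responder into a responder, never the reverse. The bias in the overall rate is upward or zero.

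**3. Size per man.** 1/50 = 2.0 percentage points. With the plan's Beta(0.33, 0.67) prior, the equal-tailed 95% interval for 17/50 is 21.8% to 47.4%, as section 11.C states. If 3 of those 17 improved only after another treatment, the count without them is 14/50 = 28%, with interval 16.8% to 41.1%.

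**4. Reproducing the plan's futility figures.** Inputs from section 11.D: stop at 0 or fewer responders of 10, 2 of 20, 5 of 30, 7 of 40. An exact binomial path through these limits treats men as fully followed at each look, in line with the enrolment hold in 11.D.

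| True response | P(stop), recomputed | Plan's table, toxicity 0.10 |
|---|---|---|
| 0.15 | 0.814 | 0.81 |
| 0.25 | 0.276 | 0.28 |
| 0.33 | 0.063 | 0.06 |

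**5. Illustration of the bias.** Let r be the true PAVE response rate. Let s be the share of PAVE non-responders who start another ED treatment and keep giving scores, and q the chance that they then cross a category.

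- Observed rate = r + (1 − r) × s × q
- Extra responders per 50 = 50 × (1 − r) × s × q

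The documents give neither s nor q. Assumed ranges: s = 2%, 5%, 10%; q = 50% to 90%. Example with r = 0.15, s = 0.05, q = 0.5: 0.15 + 0.85 × 0.05 × 0.5 = 0.171, and 50 × 0.85 × 0.05 × 0.5 = 1.06 extra responders.

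| r | s | Observed rate (q = 50% to 90%) | Extra responders per 50 | P(stop for futility) |
|---|---|---|---|---|
| 0.15 | 0 | 15.0% | 0 | 0.81 |
| 0.15 | 2% | 15.9% to 16.5% | 0.4 to 0.8 | 0.77 to 0.74 |
| 0.15 | 5% | 17.1% to 18.8% | 1.1 to 1.9 | 0.70 to 0.61 |
| 0.15 | 10% | 19.3% to 22.7% | 2.1 to 3.8 | 0.58 to 0.39 |
| 0.25 | 0 | 25.0% | 0 | 0.28 |
| 0.25 | 2% | 25.8% to 26.4% | 0.4 to 0.7 | 0.25 to 0.22 |
| 0.25 | 5% | 26.9% to 28.4% | 0.9 to 1.7 | 0.20 to 0.16 |
| 0.25 | 10% | 28.8% to 31.8% | 1.9 to 3.4 | 0.15 to 0.08 |

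**The case against.** The best defence is that the text already implies such men leave. Three places point that way, and the word *during* has a harmless reading: Table 1 runs to 18 months but has no IIEF-5 after month 12, so a drug prescribed in months 12 to 18 cannot affect response. That reading is possible and, if intended, removes the problem. It is not certain, because sections 1.0 and 11.A put participation at one year.

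Uptake may also be low, since section 2.0 calls the cost of 5-PDE inhibitors prohibitive for most patients. At 2% uptake and a true 15% response, the bias is about 0.9 to 1.5 points, against a credible interval just under 26 points wide. None of the scenarios tabulated lifts a true 15% or 25% to the 33% reference rate, and the final analysis is an estimate, not a test. All of this stands, and it limits the weight of the point.

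A reader might infer more than the documents support:

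- *That the plan has no rule at all.* The appendices and the prescribing figure were not available for this review, so the statement holds only for the supplied text.
- *That a gain after adding another drug is not due to PAVE.* The sponsor's expectation of a lower success rate does not show this. The gain cannot be attributed to either treatment.
- *That timing is certain to be lost.* The 6- and 12-month history and physical, or prescription records, may date some use. The plan does not require it.

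**Conclusion.** The point holds conditionally. In the supplied text, scores after another ED treatment count toward response, and whether men who start one remain on study is unsettled. If any do, the overall response rate is biased upward by 2 points for each man whose only gain follows the other treatment, and the futility rule becomes less likely to stop.

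The direction is certain (upward or zero). The size is not known, because every uptake and crossing rate above is an assumption. The effect is zero if all such men leave before another IIEF-5. It would be wrong to read this as a finding that the response rate will be inflated, or that the sample size, intervals or stopping limits are miscalculated: the figures checked here reproduce. It is a low-cost improvement worth making, because without a rule and start dates the sponsor could not reliably show that the bias was absent.

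**What to change.** 1. Reconcile sections 11.A, 11.B.iii and 11.E on whether a man who starts another ED treatment remains on study. That choice is the sponsor's, and no change to patient care is proposed. Use one defined term for other ED treatment throughout.
2. Add to 11.B.i, 11.D and 11.E: IIEF-5 scores obtained after the start of a non-protocol ED treatment do not count toward response; a response documented before that start stands; the patient stays in the denominator.
3. Record other ED treatment and its start date at each IIEF-5 contact (3, 6, 9 and 12 months) as well as at 18 months.
4. Report the response rate using all scores as a sensitivity analysis.

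The cost is a short scoring rule, one question at contacts that already take place, and one extra analysis. The reported rate may be lower. The rule is conservative against a late PAVE effect in men who used another treatment, even briefly. The all-scores rate shows the most that this could matter among men who keep giving scores, assuming the other treatment does not lower them. If no man starts another treatment while giving scores, the two rates coincide.

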**C. Sample Size**

A total of 50 patients will be enrolled. With 50 patients, if the response rate is 33%, then assuming an uninformative prior of beta(0.33, 0.67), the 95% credible interval would be (20.1%, 45.3%) if 16/50 respond and (21.8%, 47.4%) if 17/50 patients respond. The selection of 50 patients provides a 95% credible interval that has a width less than 26% at approximately 33%.

**D. Interim Analyses for Safety and Futility**

Interim analyses will begin after 10 patients have been enrolled. Monitoring will then be performed every 10 patients to ensure that patients are exhibiting reasonable toxicity and efficacy rates to continue with the trial. Patients who receive treatment less than 8 weeks will still be counted in toxicity and futility monitoring as long as they received at least 1 dose of the study drug. For patients already on statins, this means the patient must have started the combination. For patients who are starting on atorvastatin, patients will count as long as they received at least one dose of atorvastatin. If the trial can continue after 40 patients, then interim analyses will be complete. Adverse events will continue to be recorded and reported for all patients. If the toxicity or efficacy rates are noted to be different among the patient subgroups, the same stopping rules may be applied to any subgroup of concern to discontinue enrollment of that subgroup.

A Bayesian sequential monitoring design (Thall et al. 1995 and 1998) will be used to monitor the trial for toxicity and futility. Calculations were performed in MultcLean 2.1.

Toxicities will be monitored assuming a prior probability of toxicity following Beta(1,1) against a constant rate of 30% as the maximum acceptable toxicity rate. Trial limiting toxicities (TOX) are any grade 3 or higher toxicities at least possibly related to the study drug that occur in the first 8 weeks of therapy. The trial will be terminated if  $\text{Prob}(\text{TOX} > 0.30 \mid \text{data}) > 0.95$ . Following this rule, the trial will be terminated according to the table below once the first 10 patients have enrolled.

Similarly, efficacy will be monitored assuming a prior probability of response following Beta(0.33,0.67) against a constant rate of 33% as the minimum acceptable response rate. A patient will have a response if there is documented improvement at any time point on the trial. The trial will be terminated if  $\text{Prob}(\text{Response} < 0.33 \mid \text{data}) > 0.975$ . Following this rule, the trial will be terminated according to the following table once the first 10 patients have enrolled.

If there are this many patients treated who are evaluable (i.e., have TOX or completed the first 8 weeks without TOX for TOX, or have at least one IIEF result post-baseline for response)	10	20	30	40
Stop the trial if there are this many (or more) patients who have TOX	6	10	14	17
Stop the trial if there are this many (or fewer) patients who have responded.	0	2	5	7

The first 10 patients will be accrued before the first analysis. If 6 or more of the 10 patients have TOX events, stop the trial and the treatment will be declared as too toxic for this population. If there are 5 or fewer patients with TOX events and at least 1 patient with response, enroll the

next 10 patients and compare the number of patients with TOX and response against the table's rules.

The futility rule will be checked at the same time as the safety check even though the assessment time is later. As long it is safe and there are enough responses to continue, the trial will continue without delay. If there are not enough responses to continue but enough patients are pending response that it will be possible to continue once they are assessed, enrollment will hold until enough responses occur or enough patients go off study without response to prevent the possibility of passing the rule. Since response can occur at any of the planned times, a patient who was previously a non-responder can become a responder at a later follow-up and will count as a responder in the current analysis even if counted as non-responder in a previous analysis. A patient will not change from a responder to non-responder later.

The operating characteristics for these rules are summarized in the following table, based on simulations performed in Multc Lean Desktop version 2.1.

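### Section 11.D gives two toxicity denominators for men who stop drug before week 8 without TOX; the stopping decision can depend on which is used, so they must be reconciled

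*Combined protocol and SAP*

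**What the plan says.** Section 11.D defines a trial-limiting toxicity (TOX) as "any grade 3 or higher toxicities at least possibly related to the study drug that occur in the first 8 weeks of therapy". It monitors the TOX rate with a "prior probability of toxicity following Beta(1,1) against a constant rate of 30% as the maximum acceptable toxicity rate", and stops when the posterior probability of exceeding 30% is above 0.95. The boundaries are 6, 10, 14 and 17 men with TOX at 10, 20, 30 and 40 evaluable men.

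On who is in the denominator, Section 11.D speaks twice:

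- The text: "Patients who receive treatment less than 8 weeks will still be counted in toxicity and futility monitoring as long as they received" (a single dose suffices).
- The stopping-table header: evaluable for toxicity are men who "have TOX or completed the first 8 weeks without TOX for TOX".

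Section 11.E, on the summary report to the IND Office, uses wording close to the header: "This should be submitted every 10 evaluable patients, complete 8 weeks of study treatment". It sets when a report is due, not who is in the denominator.

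Neither statement in 11.D says how TOX status is set for a man who stops early. The protocol foresees such men. Under Section 8.G.3, if a Grade 2 toxicity of unclear origin persists through three weekly dose reductions, "all 3 drugs should be stopped and the patient should be removed from the study". Grade 2 is not itself TOX. Section 7.0.E leaves drug cost to patients or payers, and Section 11.A lets a man withdraw for any reason.

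**The concern.** A man with TOX enters the count under both statements. A man who stops early without TOX enters under the text, where the natural reading is that he counts as TOX-free, and drops out under the header if its 8 weeks are weeks of treatment. The header's denominator then depends partly on the outcome.

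This is the trial's safety stopping rule, so the same men could lead to different decisions depending on which sentence the site follows. The operating characteristics in 11.D have no term for early stopping, so they do not show how far either version departs from the stated performance.

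**Working it through.** **Inputs.** From 11.D: Beta(1,1) prior, 30% limit, cutoff 0.95, looks at 10/20/30/40, boundaries 6/10/14/17. Early-stopping rates are assumptions.

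**1. The plan's boundaries.** Take the smallest x with P(rate > 0.30 | Beta(1+x, 1+n−x)) > 0.95:

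- n=10: x=6 gives 0.978, x=5 gives 0.922
- n=20: x=10 gives 0.974, x=9 gives 0.932
- n=30: x=14 gives 0.976, x=13 gives 0.947
- n=40: x=17 gives 0.959, x=16 gives 0.921

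All four boundaries reproduce.

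**2. The plan's operating characteristics.** An exact binomial recursion over the four looks gives Pr(stop for TOX) = 0.116, 0.508 and 0.892 at true rates 0.30, 0.40 and 0.50. The plan's rows with response rate 0.55, where futility hardly acts, show 0.12, 0.51 and 0.89. Adding the futility rule, with TOX and response independent, gives 0.172 at TOX 0.30 and response 0.33 (plan: 0.17). All 25 tabulated stop probabilities agree within 0.005. They therefore assume that every man counted has a known 8-week status.

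**3. One data set, two paths.** Ten men are treated, 5 have TOX and 2 stopped early without TOX. Under the text this is 5/10, posterior 0.922, and the trial continues to 20. Under the header it is 5/8, posterior 0.975. Eight is not a scheduled look, so the site waits for two more evaluable men; one TOX among them makes 6/10, and the trial stops.

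**4. Direction of error.** Let p be the true 8-week TOX rate, d the share of treated men who stop early without TOX, and q the share of those who would have had TOX by week 8, with no later capture.

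- Text (counted as TOX-free): monitored rate = p − dq. Error = −dq, never positive, and zero if q = 0.
- Header (excluded): monitored rate = (p − dq)/(1 − d). Error = d(p − q)/(1 − d): positive if q < p, zero if q = p, negative if q > p.

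**5. Stopping unrelated to TOX.** Assume a share s stops at week 4, TOX risk is uniform over 8 weeks, and nothing is captured later. Then text rate = p(1 − s/2), and header rate = p(1 − s/2)/[p(1 − s/2) + (1 − s)(1 − p)]. For p=0.40 and s=0.20 these are 0.40×0.90 = 0.360 and 0.360/(0.360+0.480) = 0.429. For s=20%:

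| True TOX | Text rate | Header rate | Stop: full follow-up | Stop: text | Stop: header |
|---|---|---|---|---|---|
| 0.20 | 0.180 | 0.220 | 0.009 | 0.005 | 0.016 |
| 0.30 | 0.270 | 0.325 | 0.12 | 0.06 | 0.19 |
| 0.40 | 0.360 | 0.429 | 0.51 | 0.32 | 0.64 |

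At p=0.10 all three stop probabilities are below 0.001. At p=0.40, text and header give 0.41 and 0.57 for s=10%, and 0.24 and 0.72 for s=30%. A competing-hazards model with constant rates gives nearly the same for p=0.40 and 20% stopping (0.33 and 0.65).

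The header overstates here because a man TOX-free at week 4 has a remaining risk of 0.20/0.80 = 0.25, below 0.40. The header figures take all four looks as reached.

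**6. Stopping related to TOX.** Take p=0.40 and d=0.20:

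| q | Text rate | Header rate | Stop: text | Stop: header |
|---|---|---|---|---|
| 0 | 0.40 | 0.50 | 0.51 | 0.89 |
| 0.40 | 0.32 | 0.40 | 0.17 | 0.51 |
| 0.60 | 0.28 | 0.35 | 0.08 | 0.28 |

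Full follow-up gives 0.51 in every row. At q=0.60 both versions stop too seldom.

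**The case against.** Several counter-arguments have weight.

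- **The header may mean follow-up.** It does not say 8 weeks of treatment. Read as 8 weeks of follow-up, most of the conflict disappears. The TOX definition, which is tied to weeks of therapy, and the similar wording in 11.E lean the other way. The ambiguity stands and needs a sentence to settle it.
- **The target may be TOX on therapy.** For TOX occurring while on drug among all treated men, the text count is unbiased. The TOX definition allows that reading, but the plan does not state it.
- **The effect is small if the drugs are well tolerated.** Section 2.0 describes them that way, and at true TOX of 0.20 or below the choice hardly matters. It matters near and above the 30% limit, where the rule is meant to act.

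A reader might go further in two ways that the documents do not support.

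- **That the two versions always err in opposite directions.** This holds when early stoppers have some risk of later TOX, but less than the overall rate. Section 8.G.3 removes men because a toxicity has not resolved, so stoppers may well be likelier than others to develop TOX. In that case both versions understate the rate.
- **That nothing is graded once a man stops.** Section 10.0 captures serious adverse events to 30 days after the last dose, and related ones beyond that. Section 11.B.ii records adverse events at 30 days after active treatment, although its reference to one year on PAVE leaves early stoppers unclear. For a man who stops after about week 4, 30 days reaches week 8. If this capture applies, it moves the text count back toward full follow-up. It does not return excluded TOX-free men to the header's denominator.

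**Conclusion.** The point holds as an inconsistency in the definition of the toxicity denominator, reading the header as 8 weeks of treatment. The toxicity decision can turn on it, and the stated operating characteristics do not cover it.

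Measured against the 8-week TOX rate, the text version has a known direction of error (downward or none). The direction of the header version depends on why men stop, which the documents do not tell us. The sizes are illustrations: they rest on assumed early-stopping shares of 10 to 30%, on no capture after stopping, and on either uniform risk or a chosen q. Under those assumptions the gap is material at true TOX of 0.30 to 0.40 and negligible at 0.20 or below. The boundaries and tabulated operating characteristics are correct for fully observed men.

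**What to change.** Use one definition in the 11.D text and the table header, and align the 11.E report trigger with it:

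- Every man with at least one dose, as 11.D already defines it, is in the TOX denominator. His TOX status is ascertained to 8 weeks from first dose, whether on or off drug.
- Reword the header's toxicity clause to: *have TOX, or have reached 8 weeks from first dose without TOX, on or off drug*. Make the window in the TOX definition match.
- Keep men who cannot be reached in the denominator under the one-dose rule. Dropping only those without TOX would bring back an outcome-dependent denominator. Report their number at each look, and show the stopping decision with them counted as TOX-free and with them excluded.
- State that removal from the study under Section 8 does not end this safety follow-up.

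Boundaries and sample size stay as they are. The cost is wording in 11.D, 11.E and Section 8, plus a phone CTCAE assessment for men who stop early, which Table 1 already allows. A look may have to wait for an early stopper's 8-week window to close.
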